### Protocol

Up to 100 patients with chronic hepatitis B will be enrolled including at least 40 patients who have not been previously treated (naïve patients: primary study) and up to 40 patients who have received or are receiving nucleoside analogue therapy and up to 20 patients who have relapsed following withdrawal of therapy (experienced patients: salvage study). After medical evaluation and liver biopsy, patients will be randomized and receive either monotherapy with tenofovir (300 mg) daily or combination therapy with tenofovir (300 mg) and emtricitabine (FTC: 200 mg) daily. Gilead Sciences will provide the combination of tenofovir and emtricitabine as a single tablet and tenofovir 300 mg as a single tablet. Neither the investigators nor the patients will be blinded to the investigational agents. Patients will be followed carefully on therapy at 2 to 12 week intervals and undergo repeat medical evaluation and liver biopsy at 48 and 192 weeks. Therapy will be continued indefinitely, although the randomized phase of this trial will last for 192 weeks only. The definition of a successful endpoint of therapy will be the maintained suppression of HBV DNA below  $10^2$  IU/ml by current PCR-based assays, Roche Amplicor assay). Secondary endpoints will be (2) normalization of ALT levels and (3) histological improvements which are expected to occur in all patients with full suppression of HBV DNA and in a proportion of those with partial suppression. Other endpoints will be (3) loss of HBeAg and (4) loss of HBsAg. Patients who have lost HBsAg will undergo a monitored withdrawal of therapy with reinstatement of treatment if relapse occurs.

#### A1. Inclusion criteria: Primary Study (nucleoside analogue-naïve subjects)

- 1) Age >18 years and older, male or female
- 2) Known serum HBsAg positivity for 24 weeks
- 3) Detectable HBV DNA > $10^4$  IU/ml. For patients with cirrhosis HBV DNA > $10^3$  IU/ml
- 4) Serum ALT or AST levels 1.5 X ULN (for ALT:  $\geq 62$  U/L and for AST:  $\geq 46$  U/L) based on at least two determinations taken at least one month apart during the 24 weeks before study entry; no ALT requirement for patients with cirrhosis
- 5) Liver biopsy within 2 years of entry that is consistent with chronic hepatitis and with a histology activity index (HAI) score of 4 or more (scores range from 0-18) and an Ishak fibrosis score of at least 1 (scores range from 0-6). For patients who have had a liver biopsy at another institution, slides must be obtained for reading and scoring at the NIH.
- 6) Written informed consent

#### A2. Inclusion criteria: Salvage Study (nucleoside analogue experienced subjects)

- 1) Age >18 years and older, male or female
- 2) Known serum HBsAg positivity for 6 months

- 3) Detectable **HBV DNA >10^2** IU/ml.
- 4) Liver biopsy within 5 years of entry that is consistent with chronic hepatitis
- 5) Written informed consent

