Patients will be seen in the outpatient clinic at weeks 0, 2, 4, 8, 12, 24, 36, and 48 weeks during the first year of therapy and at 12 week intervals thereafter.

At 48 weeks, all patients will be readmitted to the NIH Clinical Center and undergo a repeat thorough medical evaluation and liver biopsy. Patients in the salvage arm will be excluded from undergoing the 48 week liver biopsy. Continuation of therapy thereafter will depend upon both tolerance and benefit. All patients will undergo a 192 week follow-up biopsy to assess long-term efficacy and durability of response. Benefit is described in Section F “Assessment of Response” and tolerance in Section G “Assessment of Toxicity.”

The side effects will be monitored regularly. Tenofovir and emtricitabine will be stopped if moderate side effects attributable to either or both medications develop and persist for at least one week or on repeat testing. The medication(s) can be restarted if the adverse event resolves and does not appear to be related to either or both medications.

In the absence of toxicity attributable to either agent, combination therapy with tenofovir and emtricitabine or monotherapy with tenofovir will be continued for 192 weeks. Study medication/s will be discontinued if there is serological evidence of resolution of chronic hepatitis B, as shown by loss of HBsAg, documented on two serum samples taken at least six months apart.

Patients on therapy who develop evidence of drug resistance with elevations of serum aminotransferase levels twice above normal and HBV-DNA levels greater than  $10^6$  IU/ml will be switched to alternative therapies if mutually agreed between the patient and the investigators.

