#### **F. Assessment of response:**

In this study, the combination of tenofovir and emtricitabine and tenofovir monotherapy will be evaluated for long-term effects on chronic hepatitis B in both HBeAg-positive and -negative cohorts and in treatment naïve and those with resistance to lamivudine, adefovir, entecavir or all agents.

Definitions:

- a) **Full virological response:** absence of detectable HBV DNA by PCR ( $<10^2$  IU/ml)
- b) **Partial virological response:** suppression of HBV DNA to  $<10^4$  IU/ml but  $>10^2$  IU/ml
- c) **Serological response (HBeAg-positive patients only):** loss of detectable HBeAg.
- d) **Full biochemical response:** fall of serum ALT into the normal range ( $<41$  IU/L)
- e) **Partial histological response:** improvement in liver histology as defined by a decrease in the inflammatory component of the histological activity index (HAI) score by 3 points or more and no worsening of the Ishak fibrosis score. Histological responses will be assessed after 48 and 192 weeks of therapy.
- f) **Complete histological response:** improvement in liver histology as defined by a decrease in the inflammatory component of the histological activity index (HAI) score by 3 points or more and no worsening of the Ishak fibrosis score and a decrease of the HAI score to 3 or less. Histological responses will be assessed after 48 and 192 weeks of therapy.
- g) **Combined response:** the combination of a virological, serological, biochemical and histological response.
- h) **Complete Response:** Loss of HBsAg. A complete response is the major focus and most hoped for outcome of long-term antiviral treatment of hepatitis B. A complete response is reason for stopping all antiviral treatment.

Beneficial responses are also characterized as initial, maintained or sustained:

- a) **Initial response:** full virological or biochemical response occurring within the first 24 weeks of therapy.

- b) **Maintained response:** virological, serological, biochemical, histological, or combined response present at the time of last observation in a patient still receiving therapy.
- c) **Sustained response:** virological, serological, biochemical, histological or combined response present at the time of last observation and at least six months after stopping therapy.

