The primary study endpoints will be a maintained full virological response after 48 weeks and 192 weeks of therapy (the two points of formal statistical analysis). The major secondary endpoint will be absence of a failure of therapy and absence of resistance mutations. Other endpoints to therapy will be loss of HBeAg, loss of HBsAg, normalization of serum ALT, improvements in histology activity index, improvements in hepatic fibrosis, improvement in Fibroscan scores and decrease in HVPg. Other endpoints will be improvement in symptom scores at 48 and 192 weeks.

Failure of therapy may be due to primary non-response, lack of virological response, breakthrough, or relapse, as defined below.

A **primary non-response** is defined as lack of decrease in HBV DNA levels by at least 1  $\log_{10}$  after at least 24 weeks of therapy in the absence of non-compliance.

A **failure in virological response** is defined as failure to suppress HBV DNA below  $10^4$  IU/ml after 48 weeks of therapy in the absence of non-compliance.

A **breakthrough** is defined as a  $\geq 1 \log_{10}$  IU/L increase in HBV DNA level from nadir in two consecutive samples at least one month apart in a patient with an initial full virological response in the absence of non-compliance.

A **relapse** is defined as a rise in HBV DNA levels to above  $10^4$  IU/ml or of ALT to above the normal range after therapy is stopped in a patient who previously had a maintained full virological response.

These definitions are all interlocking but help to define response and non-response rates and whether therapy has a sustained effect.

**Stopping therapy:** Therapy will be continued indefinitely or until one of the following endpoints are reached:

1. **Failure of therapy:** If HBV DNA levels remain consistently  $>10^4$  IU/ml after one year of continuous therapy, patients will be offered alternative therapy or the option to stop therapy. Alternative therapies may include switching to combination therapy if they were receiving monotherapy or switching to entecavir if receiving combination therapy. Patients who fail to respond may also elect to receive a course of peginterferon. These options are available at the NIH Clinical Center on an open-label basis.

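### Salvage patients may enter with an HAI too low for the 3-point histological response to be reachable at week 192 (minor, secondary endpoint)

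*Combined protocol and SAP*

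**What the plan says.** A1 (naïve patients) requires a biopsy "with a histology activity index (HAI) score of 4 or more" and an Ishak fibrosis score of at least 1. A2 (experienced patients) and A.3 (relapsers) require only "Liver biopsy within 5 years of entry that is consistent with chronic hepatitis". Neither the exclusion criteria nor Section C adds a minimum HAI. A.3 also requires raised ALT or AST; A2 has no such criterion.

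Section F, definition (e), sets partial histological response as a "decrease in the inflammatory component of the histological activity index (HAI) score by 3 points or more", without worsening fibrosis. Definition (f), complete histological response, adds "a decrease of the HAI score to 3 or less". Definition (g), combined response, includes a histological response as one of its parts. Section F opens by saying that the two regimens will be evaluated in naïve patients and in "those with resistance to lamivudine, adefovir, entecavir or all agents".

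On timing, Section D exempts salvage patients from the week-48 biopsy but states: "All patients will undergo a 192 week follow-up biopsy to assess long-term efficacy and durability of response". Week 192 is therefore their only planned on-study histology. Section F also lists "improvements in histology activity index" among the other endpoints, and Section I names Student's t-test for means.

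**The concern.** The response definitions suit the A1 population, whose entry floor of 4 leaves room for a 3-point fall. They are carried over to a population with no floor. A salvage patient who enters with quiet histology and is then fully suppressed for four years cannot count as a histological responder. A patient at HAI 2 on both biopsies already has the end state that definition (f) asks for, yet is counted with a patient who stays at HAI 10. This sits badly with the Protocol section, which expects histological improvement in every fully suppressed patient. Definition (c) shows that the plan can restrict a response to those able to have it: serological response applies to HBeAg-positive patients only. Definitions (e) and (f) carry no such limit.

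At stake is how the week-192 histological and combined responder rates read in any table that includes salvage patients.

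**Working it through.** **Plan's own figure.** The plan gives no rate or power for histology. Its only power figure, 86% in Section I, is for the virological endpoint (94% v 70%, 50 per arm, two-sided Fisher test at 0.05). Exact enumeration gives 85.7%, so it reproduces. HAI does not enter it.

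**Arithmetic of the rule.** Section C gives the HAI scale as 0 to 18 for inflammation and necrosis; I take the inflammatory component in Section F to be this score. The largest possible fall from baseline h is h − 0 = h.

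| Baseline HAI | Largest fall | (e) reachable | (f) reachable |
|---|---|---|---|
| 0 | 0 | no | no |
| 1 | 1 | no | no |
| 2 | 2 | no | no |
| 3 | 3 (to 0) | yes | yes |
| 4 | 4 | yes | yes |

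Three is the lowest baseline from which either definition can be met. Because (g) needs a histological response, it is closed to baselines 0–2 as well.

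**Ceiling on the responder rate.** The share u of salvage patients with HAI 0–2 is not in the documents. I assume 10%, 20% and 40%, and apply it to Groups C and D only (at most 20 + 20 = 40), because A2 lacks an ALT or AST criterion. Patients unable to respond: k = 40u. Ceiling in a set of N patients: 1 − k/N. Denominators use the group caps of 20 in Section D.

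| u (assumed) | k | All, N = 100 | Groups A–D, N = 80 | Groups C–E, N = 60 | Groups C–D, N = 40 |
|---|---|---|---|---|---|
| 10% | 4 | 96% | 95% | 93% | 90% |
| 20% | 8 | 92% | 90% | 87% | 80% |
| 40% | 16 | 84% | 80% | 73% | 60% |

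The naïve stratum stays at 100%. If the same shares held in all 60 salvage patients, k would be 6, 12 or 24 and the ceiling among 100 would be 94%, 88% or 76%.

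**Gain from adjusting HAI for baseline.** Assume equal standard deviations (SD) at baseline and week 192, and correlation r between 0.3 and 0.6; neither is in the documents. The between-arm variance is proportional to SD²(1 − r²) with adjustment, 2·SD²(1 − r) for change scores and SD² for week-192 scores.

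- Against a t-test on change: (1 − r²)/[2(1 − r)] = (1 + r)/2, which is 0.65 at r = 0.3 and 0.80 at r = 0.6.
- Against a t-test on week-192 scores: 1 − r², which is 0.91 at r = 0.3 and 0.64 at r = 0.6.

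**The case against.** The strongest reply is that histological response was never a salvage aim. Hypotheses and Issues puts both 3-point definitions under naïve patients, and defines salvage response by HBV DNA and ALT (plus HBeAg for relapsers who sero-reverted). The Background gives the salvage arm's purpose as safety and viral suppression. Section I names no histological responder test, population or power. All of this is correct. Applying (e) and (f) to salvage patients rests on Section F, whose opening sentence names resistant patients but not relapsers, and on the week-192 biopsy for everyone. What survives is that Section F states the definitions without restriction, so someone building the week-192 tables could apply them to all patients as written.

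The number affected is also unknown. The Background says that disease worsens in most patients treated on after resistance, which argues for few low scores. On the other side, A2 admits patients with HBV DNA just above 10² IU/ml, resistant patients stay on their previous drug until randomisation, and the Background links suppression below 10⁴ IU/ml with better biopsies. Low scores are plausible, but their frequency cannot be derived. In A.3 they are less likely because of the enzyme criterion.

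Finally, a mean HAI comparison is already possible, and baseline adjustment is good practice whatever the entry criteria. Both points stand. The adjustment is worth adding because it uses data already collected and keeps low-HAI patients in a histological analysis that can register their outcome.

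A reader might infer three stronger things that the documents do not support:

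- **Bias between arms.** Randomisation is stratified by previous therapy and HBeAg status, and baseline HAI precedes it, so the cap falls on both arms alike in expectation.
- **Treatment failure.** The failure categories and stopping rules in Section F contain no histological criterion.
- **A stated loss of power.** The plan has no histological planning rates. Those from the site's earlier adefovir study concern other drugs at one year, in a cohort including previously treated patients who may already have had low HAI.

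**Conclusion.** The concern holds as a minor point on a secondary endpoint. It is certain that a salvage patient entering with HAI 0–2 cannot meet definitions (e), (f) or (g) at week 192 in either arm, and that A2 and A.3 allow such a patient. It is conditional on responder rates being reported in a set that includes salvage patients. The size is unknown: 4–16 patients, and a ceiling of 96–84% among 100, follow only from the assumed 10–40% share in Groups C and D at full enrolment. The primary endpoint, its 86% power, the naïve stratum and the salvage response by HBV DNA and ALT are unaffected.

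**What to change.** In Section F, definitions (e) and (f), add: in patients with baseline HAI of 3 or more. Report that denominator by arm, which would also show any chance imbalance. Repeat with a cutoff of 4, matching A1, as a sensitivity analysis.

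In Section I, replace the unadjusted t-test for HAI by a comparison of week-192 HAI between arms adjusted for baseline HAI, in all patients with both biopsies. Report the number with missing biopsies by arm, because this comparison is limited to those biopsied while Section I counts missing patients as failures for response.

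The cost is one phrase in each definition and two sentences in Section I. No procedure, data item or eligibility criterion changes. The downside is that the few patients with baseline HAI 0–2 leave the responder table; those with both biopsies stay in the HAI comparison.

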### A.3 Inclusion criteria: Salvage Study (relapsers)

- 1) Age >18 years and older, male or female
- 2) Known serum HBsAg positivity for 6 months
- 3) Detectable **HBV DNA >10^3** IU/ml.
- 4) Liver biopsy within 5 years of entry that is consistent with chronic hepatitis
- 5) Written informed consent
- 6) Serum ALT or AST levels 1.5 X ULN (for ALT:  $\geq 62$  U/L and for AST:  $\geq 46$  U/L) based on at least two determinations taken at least 2 weeks apart

### B. Exclusion criteria

- 1) Previous or current treatment with tenofovir or emtricitabine.
- 2) Co-infection with HDV as defined by the presence of anti-HDV in serum and/or HDV antigen in the liver.
- 3) Co-infection with HCV as defined by the presence of HCV RNA in serum.
- 4) Co-infection with HIV as defined by the presence of anti-HIV in serum.
- 5) Decompensated liver disease as defined by serum bilirubin >2.5 mg/dL (with direct bilirubin > 0.5 mg/dL), prothrombin time of greater than 2 seconds prolonged, a serum albumin of less than 3 g/dL, or a history of ascites, variceal bleeding or hepatic encephalopathy.
- 6) Presence of other causes of liver disease, (i.e. hemochromatosis, Wilson disease, alcoholic liver disease, nonalcoholic steatohepatitis, alpha-1-anti-trypsin deficiency).
- 7) A history of organ transplantation or in the absence of organ transplantation, any immunosuppressive therapy requiring the use of more than 5 mg of prednisone (or its equivalent) daily.
- 8) Significant systemic illness other than liver diseases including congestive heart failure, renal failure, chronic pancreatitis, diabetes mellitus with poor control that in the opinion of the investigator may interfere with therapy.
- 9) Pregnancy or inability to practice contraception in patients capable of bearing or fathering children and lactating women.
- 10) Hepatocellular carcinoma (HCC), or the presence of a mass on imaging studies of the liver that is suggest of HCC, or an alpha-fetoprotein level of greater than 500 ng/mL.
- 11) History of clinically apparent pancreatitis or evidence of subclinical pancreatitis as shown by serum amylase values twice the upper limits of the normal range and abnormalities of the pancreas on CT or other imaging studies of the abdomen.
- 12) Sensory or motor neuropathy apparent from medical history and physical examination.
- 13) Creatinine clearance < 50 ml/min, serum creatinine > 1.3 mg/dl or urine protein >1 gram/24-hours; creatinine clearance will be determined on the average of two 24 hour urine specimens. Accuracy of collection will be ensured by documenting

- appropriate total creatinine excretion in the 24-hour urine specimen (15 mg/kg) and correcting for the patient's age, gender and body surface area.
- 14) Concurrent use of nephrotoxic agents (e.g., aminoglycosides, amphotericin B, vancomycin, foscarnet, cis-platinum, pentamidine, nonsteroidal anti-inflammatory agents) or competitors of renal tubular excretion (e.g., probenecid) within 2 months prior to study screening or the expectation that the subject will receive these during the course of the study.
  - 15) History of hypersensitivity to nucleoside analogues.
  - 16) Active ethanol/drug abuse/psychiatric problems such as major depression, schizophrenia, bipolar illness, obsessive-compulsive disorder, severe anxiety, personality disorder that, in the investigator's opinion, might interfere with participation in the study.
  - 17) History of renal tubular acidosis.
  - 18) History of malignancy or treatment for a malignancy within the past 5 years.
  - 19) Presence of conditions that, in the opinion of the investigators, would not allow the patient to be followed in the current study for at least 5 years.

### C. Initial evaluation

Patients will be seen in the outpatient clinic of the NIH Clinical Center and undergo the following evaluation before starting therapy. Patients requiring a liver biopsy will be admitted to the Clinical Center for a percutaneous liver biopsy under ultrasound guidance.

1. History and physical examination.
2. Blood tests – complete blood count (CBC with differential and platelet count), prothrombin time, partial thromboplastin time, sedimentation rate, Chem-20 (which includes alanine aminotransferase [ALT], aspartate aminotransferase [AST], direct and total serum bilirubin, albumin, total protein, lactic dehydrogenase [LDH] creatine phosphokinase [CK], sodium, chloride, bicarbonate, potassium, blood urea nitrogen, creatinine, uric acid, calcium, and phosphorus), alpha-fetoprotein, amylase, lipase, immunoglobulin G, A and M, thyroid stimulating hormone (TSH), antinuclear antibody (ANA), rheumatoid factor, lipid panel (triglycerides, total cholesterol, high density lipoprotein associated cholesterol, low density lipoprotein associated cholesterol), hepatitis B viral markers (HBsAg, anti-HBs, HBeAg, and anti-HBe), anti-HCV, anti-HDV, and anti-HIV. An additional 10 ml. of serum will be collected and stored at –20 degrees Celsius for future research testing.
3. Baseline HBV DNA level by quantitative PCR (Amplicor™: Roche, lower limit of detection 20 IU/ml) and HBV genotyping (HBV Genotyping Line Probe Assay, Innogenetics, Belgium).
4. Routine urinalysis, random total protein/creatinine ratio, and two 24-hour urines for creatinine clearance and protein excretion.
5. Pregnancy test for women of childbearing potential.
6. Patients who have not had them within the previous year will undergo chest X-ray, electrocardiogram (EKG), and abdominal ultrasound.

7. Patients will undergo percutaneous liver biopsy unless they have had one within the past two years that is available for analysis or have specific contraindications to liver biopsy. Patients with known or suspected portal hypertension (previous liver biopsy showing Ishak stage 5 or 6 or platelet count less than 100,000) will undergo a transjugular liver biopsy with measurement of the hepatic venous pressure gradient (HVPG). The liver biopsy will be scored by an expert hepatopathologist blinded to the clinical information using the Ishak modification of the histology activity index (HAI) for inflammation and necrosis (scores ranging from 0 to 18). A fibrosis score using the Ishak staging of fibrosis (0-6) will also be assigned to each liver biopsy specimen. Slides will also be stained for HBsAg, HBcAg, and HDV antigen by peroxidase-antiperoxidase techniques and scored as 0, 1, 2 or 3+ based upon the percent of cells reactive for each viral antigen. Liver-infiltrating T cells will be isolated and assessed for frequency, function and HBV-specificity by Elispot and/or flow cytometry. m-RNA levels of T cell markers and chemokines/cytokines will be quantitated by real-time PCR.
8. Patients identified with portal hypertension (HVPG > 5 mm Hg) will undergo upper endoscopy for evaluation of endoscopic varices. Management of varices will be as per the standard guidelines of the American Association for the Study of Liver Diseases.
9. Fifty milliliters of whole blood will be drawn for baseline immunological studies: CD4+ and CD8+ T cell HBV specific responses.
10. Patients will undergo an ultrasound based fibroscan that measures elasticity of the liver and is an indirect measure of degree of liver fibrosis.
11. At baseline, all patients will undergo a three-phase computerized tomography of the abdomen to fully exclude the presence of hepatocellular carcinoma and provide a baseline assessment of all patients.
12. Patients will undergo a bone mineral density scan as a baseline to monitor for bone loss. Patients found to have osteoporosis or osteomalacia at baseline will be offered therapy with bisphosphonates and calcium.

